10.6.4.3. Adverse Events

Adverse Events

AEs of Special Interest

Adverse events of special interest are classified as follows:

- Thrombosis and/or tissue ischemia secondary to excessive erythropoiesis
- Cardiomyopathy
- Pulmonary artery hypertension
- Cancer-related mortality and tumor progression and recurrence
- Esophageal and gastric erosions
- Proliferative retinopathy, macular edema, choroidal neovascularization
- Exacerbation of rheumatoid arthritis
- Worsening of hypertension

Potential AESIs will be identified through a pre-defined terms of interest process in which predefined lists of AE preferred terms corresponding with each AESI will be used to identify events considered to be potential AESIs. Sites will be prompted via query to complete any necessary additional information for these AESIs in the eCRF.

For the category of thrombosis and/or tissue ischemia secondary to excessive erythropoiesis, after the terms of interest list has been applied, the additional Hgb criteria described below will be applied to identify only those events that are considered to be secondary to excessive erythropoiesis as meeting the AESI definition for thrombosis and/or tissue ischemia secondary to excessive erythropoiesis.

Thrombosis and tissue ischemia events will be considered to be secondary to excessive erythropoiesis if during the window of [AE start date – 30 days, AE start date +15 days] any one of the following 3 events occurs:

- Any Hgb value \geq 13 g/dL (measured pre-dialysis)
- Hgb increase > 2 g/dL over 2 weeks (+1 week)
 - Note: for programming purposes, a +1 week window is applied, corresponding to the allowable visit window, to look for increases > 2 g/dL over 3 weeks
- Hgb increase > 4 g/dL over 4 weeks (+1 week)
 - Note: for programming purposes, a +1 week window is applied, corresponding to the allowable visit window, to look for increases > 4 g/dL over 5 weeks

To identify Hgb increases that meet the increase criterion above, all Hgb values taken within [AE start date – 58 days, AE start date + 15 days] will be identified. This corresponds to identifying Hgb

200807

Adverse Events

values that occurred 4 weeks before the [AE start date – 30 days, AE start date +15 days] window of interest. HemoCue Hgb and central laboratory Hgb values will then be evaluated separately to identify increases, so that HemoCue and central laboratory Hgb values are not compared to each other to identify an increase.

For HemoCue Hgb and separately for central laboratory Hgb values, if there is a Hgb value (or daily Hgb average) within the [AE start date – 30 days, AE start date +15 days] window and an earlier Hgb value (or daily Hgb average) that is within the larger [AE start date – 58 days, AE start date + 15 days] window, and the amount of time between the two Hgb values is:

- Between 1 day and 3 weeks, inclusive, then the Hgb values will be compared to determine if there has been a Hgb increase > 2g/dL.
- Between 15 days and 5 weeks, inclusive, then the Hgb values will be compared to determine if there has been a Hgb increase > 4g/dL.

Unscheduled Hgb values will also be used in the assessment of secondary to excessive erythropoiesis following the guidance specified in Section 10.6.3 for unscheduled Hgb values and multiple Hgb values on the same date.

Pre-defined Lists of AE Preferred Terms Corresponding with Each AESI

Thrombosis and/or tissue ischemia secondary to excessive erythropoiesis

- Narrow SMQ: Embolic and thrombotic events, arterial
- Narrow SMQ: Embolic and thrombotic events, venous
- Narrow SMQ: Embolic and thrombotic events, vessel type unspecified and mixed arterial and venous
- Broad SMQ: Thrombophlebitis
- Additional Preferred Terms:
 - Vascular access site occlusion
 - Vascular access site complication
 - Retinal vascular occlusion
 - Administration site ischaemia
 - Anterior segment ischaemia
 - Application site ischaemia
 - Biliary ischaemia
 - Bone marrow ischaemia
 - Brain stem ischaemia
 - Catheter site ischaemia
 - Cerebellar ischaemia
 - Cerebral ischaemia
 - ECG signs of myocardial ischaemia
 - Gastrointestinal ischaemia
 - o Graft ischaemia
 - Hepatic ischaemia

- Stoma site ischaemia
- o Subendocardial ischaemia
- o Uterine ischaemia
- o Vaccination site ischaemia
- o Vestibular ischaemia
- o Cerebral small vessel ischaemic disease
- o Colitis ischaemic
- o Delayed ischaemic neurological deficit
- Hypoxic-ischeaemic encephalopathy
- Ischaemic cardiomyopathy
- Ischaemic cerebral infarction
- Ischaemic contracture of the left ventricle
- o Ischaemic enteritis
- o Ischaemic gastritis
- Ischaemic heart disease prophylaxis
- Ischaemic hepatitis

0

0

0

0

0

0

0

0

0

0

200807

Adverse	Events

- Implant site ischaemia 0
 - Infusion site ischaemia 0
 - Injection site ischaemia 0
 - Intestinal ischaemia 0
 - Ischaemia 0
 - Macular ischaemia
 - Medical device site ischaemia
 - Myocardial ischaemia 0
 - Peripheral ischaemia 0
 - Renal ischaemia
 - Retinal ischaemia
 - Spinal cord ischaemia 0

Cardiomyopathy

Narrow SMQ: Cardiomyopathy

Pulmonary artery hypertension

- High Level Term: Pulmonary hypertensions
- Additional Preferred Terms:
 - Right ventricular dilatation
 - Right ventricular dysfunction
 - Right ventricular ejection fraction decreased

Cancer-related mortality and tumor progression and recurrence

- Narrow SMQs:
 - Biliary malignant tumours
 - Biliary tumours of unspecified malignancy
 - Breast malignant tumours
 - Breast tumours of unspecified 0 malignancy
 - Liver malignant tumours 0
 - Liver tumours of unspecified malignancy 0
 - Malignancy related conditions
 - Haematological malignant tumours
 - Non-haematolgoical malignant tumours 0
 - Haematological tumours of unspecified malignancy
 - Non-haematological tumours of 0 unspecified malignancy
 - Malignant lymphomas
- Additional Preferred Terms:
 - Aplastic anaemia

- Myelodysplastic syndrome 0
- Oropharyngeal neoplasms 0
- Ovarian malignant tumours
- o Ovarian tumours of unspecified malignancy
- Prostate malignant tumours 0
- Prostate tumours of unspecified 0 malignancy
- Tumour lysis syndrome 0
- Skin malignant tumours
- Skin tumours of unspecified malignancy 0
- Uterine and fallopian tube malignant tumours
- o Uterine and fallopian tube tumours of unspecified malignancy
 - Pancytopenia 0

- o Right ventricular enlargement
- 0

Ischaemic limb pain

Ischaemic nephropathy

Ischaemic neuropathy

Ischaemic pancreatitis

Ischaemic skin ulcer

Ischaemic stroke

Necrosis ischaemic

• Ocular ischaemic syndrome

• Optic ischaemic neuropathy

Transient ischaemic attack

Reversible ischaemic neurological deficit

Ischaemic mitral regurgitation

- Right ventricular hypertrophy
- 0
- Right ventricular failure

Adverse Events			
 Cytopenia 	0	Aplasia pure red cell	
 Myelosuppression 			
Esophageal and gastric erosions			
High Level Terms:			
 Duodenal ulcers and perforation 	0	Oesophageal ulcers and perforation	
 Gastric ulcers and perforation 	0	Peptic ulcers and perforation	
 Gastrointestinal ulcers and perforation, site 			
unspecified			
Additional Preferred Terms:	_	Heliophaeter duadanitia	
 Haematemesis Gastrointestinal haemorrhage 	0	Helicobacter duodenitis Helicobacter gastritis	
 Gastrointestinal naemorrnage Upper gastrointestinal haemorrhage 	0	Melaena	
	0	Meldena	
Proliferative retinopathy, macular edema, choroidal ne	eovas	scularization	
Bread CMO: Defined disorders			
Broad SMQ: Retinal disorders			
Exacerbation of rheumatoid arthritis			
High Level Term: Rheumatoid arthropathies			
Additional Preferred Terms:			
• Rheumatoid factor increased •	Rhe	eumatoid factor quantatative increased	
 Rheumatoid factor positive 			
Worsening of hypertension			
Narrow SMQ: Hypertension			
Blood Pressure Events			
BP events will be identified during the study via progra			
entered into the eCRF (using the narrow SMQ for hyp			
an additional BP Exacerbation eCRF page to be completed that characterizes the event as			
clinically significant and/or symptomatic.			
In addition, subjects that experience BP values that m	In addition, subjects that experience BP values that meet the following criteria at any visit will also		
be considered to have a BP event and be required to complete the Blood Pressure Exacerbation			
eCRF page:			
 SBP: an increase from baseline of ≥ 25 mmH 	lg or	SBP \geq 180 mmHg	
 DBP: an increase from baseline of ≥ 15 mmH 	la or	$DBP > 110 \; mmHc$	
	19 01		

200807

Adverse Events

BP-related SAEs are those SAEs that have been identified via the BP Exacerbation eCRF page.

False Discovery Rate (FDR) Method and Procedure

The FDR method adjusts p-values within a group (SOC or preferred terms (PTs) within a SOC) based on the following:

- a) Order p-values from lowest to highest (1... m)
- b) Compute adjusted p-values, p', as follows

p'(m) = p(m) i.e., the adjusted p-values for the highest p-value is the same as the highest p-value

 $p'(j) = min(\{p'(j+1), m/j^*p(j)\} \text{ for } j \le m - 1$

The FDR procedure is applied at the system organ class (SOC) level and for each AE preferred term (PT) reported as Tier 2 events. The following stops will be undertaken in this procedure:

- 1. Compute adjusted p-values for PTs within each SOC using the FDR method.
- 2. Order SOCs (small to large) according to the minimum FDR adjusted p-value observed for treatment differences across PTs within SOC.
- 3. Perform the FDR method on the minimum adjusted p-values from Step 2.
- 4. Select SOCs with FDR adjusted p-value from Step 3 <0.10.
- 5. Apply a single FDR adjustment to all unadjusted p-values belonging to all PTs from SOCs identified in Step 4. with a threshold of FDR adjusted p-values <0.10 will be used to flag PTs that warrant further investigation.

Note that 0.10 is recommended as a reasonable multiplicity adjustment for 0.05.

General Definitions	
 Post-Randomization last contact date for censoring (subjects not having AE) will be defined as the study completion date. 	
 Treatment emergent last contact date for censoring (subjects not having AE) will be defined as follows: 	
 1 day after the last non-zero dose date (last non-zero dose date + 1) for subjects not having treatment emergent AE and continuing on study past (last non-zero dose date + 1) 	
 Last non-zero dose date for all other subjects 	
AE Patient Years: (Cumulative total of time to AE for subjects who have the AE +	

200807

Advers	se Events
	Cumulative total of censoring time for subjects without the AE) / 365.25
	 For treatment emergent AEs, the start date of the patient years value for each subject should be the treatment start date.
	 For post-randomization AEs, the start date of the patient years value for each subject should be the randomization date.
	 For follow-up AEs, the start date of the patient years value for each subject should be 2 days after the last non-zero dose date (last non-zero dose date + 2).
•	Incidence Rate (per 100 patient years): (100 * Number of subjects with at least 1 AE) / AE person years
٠	For the analysis of the time to AE onset/worsening, if the AE onset/worsening date is missing then the time to AE onset/worsening will be counted as 1 day.
10.6.4	.4. Laboratory Parameters

Laboratory Parameters

•	If a laboratory value which is expected to have a numeric value for summary purposes, has a non-detectable level reported in the database, where the numeric value is missing, but typically a character value starting with ' <x' '="" or="">x' (or indicated as less than x or greater than x in the comment field) is present, the number of significant digits in the observed values will be used to determine how much to add or subtract in order to impute the corresponding numeric value. • Example 1: 2 Significant Digits = '< x' becomes $x - 0.01$ • Example 2: 1 Significant Digit = '> x' becomes $x + 0.1$ • Example 3: 0 Significant Digits = '< x' becomes $x - 1$</x'>
•	If there is more than one laboratory value on the same date for the same laboratory test, then the laboratory values associated with scheduled visits will be used. Hgb summaries and analyses are an exception and should use the data handling conventions outlined in Section 10.6.3.
•	 For purposes of flagging worst-case post baseline laboratory values: If there are multiple scheduled values on the same day, or only multiple unscheduled values on the same day, then the average of the values on that day should be used for the purpose of determining the worst-case value.
•	 The following will be used to convert laboratory values from SI units to conventional units [Iverson, 2007]: MCHC and Albumin: Divide the g/L value by 10 to get the g/dL value. Albumin corrected calcium: Divide the mmol/L value by 0.25 to get the mg/dL value. Phosphate: Divide the mmol/L value by 0.323 to get the mg/dL value. BUN: Divide the mmol/L value by 0.357 to get the mg/dL value. Total cholesterol, LDL-C and HDL-C: Divide the mmol/L value by 0.0259 to get the mg/dL value.

200807

Laboratory Parameters	
No	rmal Range Categories, PCI Criteria Categories and Worst Case Values
•	Normal range categories are: To Low, To Normal or No Change, To High
•	PCI criteria categories are: To Low, To w/in Range or No Change, To High
•	Subjects with a missing baseline value are to be assumed to have a normal/within range baseline value.
•	The determination of the worst-case post baseline value takes into account both planned and unscheduled assessments.
•	Worst case can be either High or Low.
	 If a subject has both a decrease 'To Low' and an increase 'To High', then the subject is counted in both the 'To Low' and 'To High' categories.
	 If a subject was High at baseline and decreases to Low during the time interval, then the subject is counted in the 'To Low' category. Likewise, if a subject was low at baseline and increases to high during the time interval, then the subject is counted in the 'To High' category.
	 Subjects are only counted in the 'To Normal or No Change' or 'To w/in Range or No Change' category if their values are:
	 When using normal ranges: Normal at baseline and have no high and no low values; When using PCI ranges: Within range at baseline and have no high and no low values
	 High at baseline and do not change to low
	 Low at baseline and do not change to high

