8.2.4.2. Planned Adverse Event Safety Statistical Analyses

AESIs & PhRMA SPERT Adverse Event Analyses

Adverse events of special interest are described in Section 10.6.4.

Summaries of AESIs will include the number, percentage and rate per 100 person-years of subjects having at least one occurrence, the number of events, the number of subjects by number of occurrence, the characteristics of the AE (serious, drug-related, etc.), outcome, maximum intensity, time to first onset/worsening, and action taken summarized by treatment group. For each count, a subject will be summarized as follows:

- Serious/drug-related/severe/fatal: If any specific AE falls in the respective category, the subject will be counted in that category.
- Outcome: The subject will be counted within a category if there is at least one specific AE in that category.
- Maximum intensity: The specific AE with the maximum intensity will be counted for this purpose. For example, a subject will be counted in the 'severe' category if there is at least one specific AE with severe intensity. A subject will be counted in the 'moderate' category if there is at least one specific AE with moderate intensity and there is no specific AE with severe intensity.
- Time to first onset/worsening (days): The earliest of onset dates for the specific AE treatment start + 1

If the AE onset date/AE worsening and/or resolution date is missing or incomplete in the database for any occurrence of the specific AE, time to first onset/worsening will be left missing for the subject. These summaries of special interest AEs will be provided for those AEs classified as treatment emergent.

Cumulative incidence function (CIF) plots may be produced for each AESI summarizing the time to first occurrence of the AESI by treatment group. If there are less than 20 subjects total for both the daprodustat and rhEPO arm, then these plots will not be created. Competing risks for the AESI cumulative incidence plots include:

AE of Special Interest (Event of interest)	Competing Risk Events
Thrombosis and/or tissue ischemia secondary	Death due to any cause prior to the AESI
to excessive erythropoiesis	
Cardiomyopathy	Death due to any cause prior to the AESI
Pulmonary artery hypertension	Death due to any cause prior to the AESI
Cancer-related mortality and tumor progression	All other non-cancer-related death prior to the
and recurrence	AESI (use death date as the competing risk
	date)

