10.4.1.4. Treatment States for AE Data

Non-serious AEs and serious AEs are to be recorded on the eCRF starting at the placebo run-in phase. Serious AEs assessed as related to study procedures or related to a GSK concomitant medication are to be recorded on the eCRF from the time a subject consents

200807

to participation in the study. AE of worsening of an on-going event will be counted once in a particular treatment state.

Treatment State	Definition
Pre-treatment	 For subjects with a non-missing screen failure date, if AE onset is on or before the screen failure date: AE Start Date ≤ Screen Failure Date For randomized subjects with a missing treatment start date, all AEs are considered pre-treatment For randomized subjects with a non-missing treatment start date, if AE onset date is before treatment start date: AE Start Date < Treatment Start Date
Placebo Run-In	If AE onset date or AE worsening date is on or after placebo run-in treatment start date & on or before placebo run-in treatment stop date: Placebo Run-in Treatment Start Date \leq AE Start Date \leq Placebo Run-in Treatment Stop Date Placebo Run-in Treatment Start Date \leq AE Worsening Date \leq Placebo Run-in Treatment Stop Date AE worsening during placebo run-in will be defined relative to the maximum intensity of AE prior to placebo run-in start date. AE worsening date is the first date in the placebo run-in period, when AE intensity increased relative to the maximum intensity of the AE prior to placebo run-in start date.
Post- randomization	If AE onset date or AE worsening date is on or after the randomization date Randomization date ≤ AE Start Date Randomization date ≤ AE Worsening Date AE worsening during post-randomization will be defined relative to the maximum intensity of AE prior to randomization date. AE worsening date is the first date in the post-randomization period, when AE intensity
Treatment emergent	increased relative to the maximum intensity of the AE prior to randomization date. If AE onset date or AE worsening date is on or after treatment start date & on or before the last non-zero dose date plus 1 day. Treatment Start Date ≤ AE Start Date ≤ Last Non-Zero Dose Date + 1 day Treatment Start Date ≤ AE Worsening Date ≤ Last Non-Zero Dose Date + 1 day AE worsening during treatment emergent will be defined relative to the maximum intensity of AE prior to randomized treatment start date.

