	AE worsening date is the first date in the treatment emergent period, when AE intensity increased relative to the maximum intensity of the AE prior to randomized treatment start date.
Follow-up	If AE onset date or AE worsening date is after the last non-zero dose date plus 1 day. AE Start Date > Last Non-Zero Dose Date + 1 day AE Worsening Date > Last Non-Zero Dose Date + 1 day AE worsening during follow-up will be defined relative to the maximum intensity of AE prior to randomized treatment start date.
Onset /Worsening Time Since 1 st Dose (Days)	AE worsening date is the first date in the follow-up period, when AE intensity increased relative to the maximum intensity of the AE prior to randomized treatment start date. If Treatment Start Date > AE Onset Date = AE Onset Date - Treatment Start Date If Treatment Start Date ≤ AE Onset Date = AE Onset Date - Treatment Start Date +1 If Treatment Start Date > AE Worsening Date = AE Worsening Date - Treatment Start

200807

Treatment State	Definition
	Date If Treatment Start Date ≤ AE Worsening Date = AE Worsening Date - Treatment Start
	Date +1 Missing otherwise.
Onset/Worsening Time Since Last	If Last Non-Zero Dose Date \leq AE onset date: AE onset date – last non-zero dose date +1
Dose (Days)	If Last Non-Zero Dose Date > AE onset date: AE onset date – last non-zero dose date If Last Non-Zero Dose Date ≤ AE worsening date: AE worsening date – last non-zero dose date +1
	If Last Non-Zero Dose Date > AE worsening date: AE worsening date – last non-zero dose date Missing otherwise.
Duration (Days)	AE Resolution Date – AE Onset Date/AE Worsening Date + 1
Drug-related	If relationship is marked 'YES' on eCRF or if the value is missing.

NOTES:

• AEs that occur or worsen during interruptions of randomized study treatment will be classified as treatment emergent and post-randomization.

• If the last non-zero dose date is missing and the treatment start date is non-missing and the AE onset date or AE worsening date is on or after the treatment start date, then the AE will be considered to be treatment emergent.

- If AE onset date or AE worsening date is missing and AE resolution date is before the treatment start date, then
 the AE will be classified as Pre-treatment. If the AE resolution date is after the start of placebo run-in, the AE will
 also be considered a Placebo Run-in AE.

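### For thrombosis/ischemia AEs that are treatment emergent only by worsening, the AESI Hgb windows stay on the pre-treatment AE start date

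*SAP*

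**What the plan says.** **Treatment emergence (10.4.1.4).** There are two routes. One is by onset: "Treatment Start Date ≤ AE Start Date ≤ Last Non-Zero Dose Date + 1 day". The other is by worsening: "Treatment Start Date ≤ AE Worsening Date ≤ Last Non-Zero Dose Date + 1 day". Worsening is judged against the event's state before randomized treatment: "AE worsening date is the first date in the treatment emergent period, when AE intensity increased relative to the maximum intensity of the AE", where the reference is the maximum intensity before that treatment began. Pre-treatment events are in the data, because "Non-serious AEs and serious AEs are to be recorded on the eCRF starting at the placebo run-in phase".

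**AESI test (10.6.4.3).** After the term list is applied, a thrombosis or ischemia event becomes an AESI "if during the window of [AE start date – 30 days, AE start date +15 days] any one of the following 3 events occurs". The three Hgb events are a value of at least 13 g/dL, a rise of more than 2 g/dL over 2 weeks, and a rise of more than 4 g/dL over 4 weeks, each rise with one extra week allowed. To find rises, "all Hgb values taken within [AE start date – 58 days, AE start date + 15 days] will be identified". The later value of a pair counts only "if there is a Hgb value (or daily Hgb average) within the [AE start date – 30 days, AE start date +15 days] window". The worsening date is not mentioned, and no other section gives a rule for worsened events.

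**Use (8.2.4 and 8.2.4.2).** Treatment-emergent AESIs are summarized and form the Tier 1 comparison between arms. One summary line reads "Time to first onset/worsening (days): The earliest of onset dates for the specific AE", followed by treatment start + 1.

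**The concern.** The analysis set is defined by two dates and the classification rule uses only one of them. An event that enters the set through its worsening date is classified on Hgb around a different, earlier date, at which the subject was in screening or run-in and still on the previous ESA.

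The category is meant to pick out events that follow an excessive Hgb response. For a worsened event the rule can err in both directions. High Hgb on daprodustat or rhEPO just before the worsening is never looked at. A high or fast-rising Hgb before treatment is looked at, and if it qualifies the event, the event is counted in the treatment-emergent Tier 1 comparison.

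**Working it through.** **Inputs.** All come from the SAP: windows of -30/+15 and -58/+15 days (10.6.4.3); emergence by onset or worsening (10.4.1.4); Treatment Day numbering without a Day 0 (10.6.1); a 4-week run-in (section 1); the visit schedule (10.2.1.1).

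**The plan's own figure.** The longer look-back is described as 4 weeks before the 30-day window: 30 + 4 × 7 = 58 days. This reproduces.

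**Step 1: window for an event emergent only by worsening.** Let treatment start be day 0 and AE start be day s. Such an event has s ≤ -1, and its window is [s - 30, s + 15].

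| AE start, s | Window | Days after treatment start covered |
|---|---|---|
| -28 | -58 to -13 | 0 |
| -21 | -51 to -6 | 0 |
| -14 | -44 to +1 | 1 |
| -7 | -37 to +8 | 8 |
| -1 | -31 to +14 | 14 |

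The latest possible close is -1 + 15 = 14 days after treatment start. Because 10.6.1 numbers the treatment start date as Day 1, that is Treatment Day 15. If s < -15, then s + 15 < 0 and every Hgb value tested is pre-treatment.

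**Step 2: comparison with a window on the worsening date w.** That window is [w - 30, w + 15], which is 46 days. Against the most favourable start-anchored window (s = -1, days -31 to +14), the overlap is 14 - (w - 30) + 1 = 45 - w days, floored at 0.

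- w = 1: 44 of 46 days.
- w = 28: 17 of 46 days.
- w ≥ 45: none.

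For worsening on day 84 the tested window ended at least 84 - 14 = 70 days earlier; on day 364, at least 350 days earlier.

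**Step 3: what on-treatment Hgb can fall inside.** The first scheduled value after Day 1 is the Week 2 HemoCue, at 14 ± 3 days, so day 11 at the earliest. It can lie in the window only if s + 15 ≥ 11, that is s ≥ -4 (taking treatment to start at the Day 1 visit, with the visit held in its allowed window). Earlier onsets can reach on-treatment Hgb only through unscheduled values, and only if s ≥ -14.

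**Step 4: an illustration.** Onset is 25 days before treatment, worsening is 200 days after it, and Hgb is 13.5 g/dL on day 195. The window tested is -55 to -10. The value on day 195 is not considered, and the event is not an AESI unless a pre-treatment value qualifies it. A worsening-anchored window would be 170 to 215 and would include it.

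**Step 5: the time line in 8.2.4.2.** Its label covers onset and worsening, but its wording uses onset dates only. Read as onset minus treatment start + 1 (the minus sign seems lost in text extraction), the illustration gives -25 + 1 = -24 days. Section 10.4.1.4 already has a worsening formula, worsening date minus treatment start + 1, which gives 201.

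**The case against.** **Onset is the right causal anchor.** A thrombosis that formed before treatment was not caused by an Hgb value months later, and an upgrade in intensity is not a new thrombosis. A new episode entered as a new AE gets its own start date and window. This would carry weight if worsened events were left out of the treatment-emergent AESIs, but they are kept in. Under the same rule, a run-in excursion on the previous ESA can then be counted as an AESI emerging on randomized treatment, which a causal argument for onset does not justify.

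**The scope is narrow.** This stands. AEs are generally recorded only from the 4-week run-in. An affected event must begin then (or earlier, for the limited SAEs collected from consent), stay the same AE, worsen on treatment, and give a different answer under the two anchors. Scheduled pre-treatment Hgb is taken only at Week -8, Week -4 and Day 1.

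**The consequences are limited.** This also stands. The Tier 1 comparison is nominal and unadjusted, and the rule is the same in both arms. Worsened AEs remain in the general treatment-emergent tables, and adjudicated thromboembolic events are analysed separately.

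**Stronger readings to avoid.** A reader might infer that worsened events are never judged on Hgb under randomized treatment. Step 3 shows that late run-in onsets can be, for up to 14 days. A reader might also infer that time to event is wrong throughout for worsened AEs. Section 10.4.1.4 already handles the worsening date, so 8.2.4.2 shows only a mismatch between label and wording.

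**Conclusion.** The point holds. For thrombosis/ischemia AEs that are treatment emergent only by worsening, 10.6.4.3 applied as written tests Hgb at the wrong time relative to the event being counted. This is a stated rule giving a misplaced result, not merely an unstated detail. For any worsening 45 or more days after treatment start, the tested window shares no day with one placed around the worsening.

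The size is minor. The SAP gives no number of affected events, and it is probably small. How often pre-treatment Hgb would wrongly qualify an event is also unknown, since the SAP does not state the Hgb entry range. The documents do not support a claim that the Tier 1 comparison is biased toward either arm.

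The conclusion assumes that a worsened event keeps its original start date alongside a separate worsening date, which is how 10.4.1.4 and the partial-date rules in 10.7.2.1 treat it.

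**What to change.** In 10.6.4.3, state that both Hgb windows (-30/+15 and -58/+15 days) are anchored on the date that makes the AE treatment emergent: the worsening date if it is emergent by worsening only, and the start date otherwise. The pairwise rule for rises should refer to the same anchor.

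As a minor alignment, reword the time line in 8.2.4.2 to use the earliest treatment-emergent onset or worsening date, following the formula in 10.4.1.4.

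The cost is one sentence in each section and a small programming change. The worsening date is already derived, so no new data are needed.

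### The Hgb look-back for the thrombosis/ischemia AESI stops at day -58, 7 days short of what the plan's own 5-week >4 g/dL criterion needs, so a small set of qualifying rises can be missed

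*SAP*

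**What the plan says.** SAP section 10.6.4.3 (AEs of Special Interest) treats a thrombosis or tissue ischemia event as secondary to excessive erythropoiesis if any one of three Hgb findings occurs in the window from 30 days before to 15 days after AE start:

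- any pre-dialysis Hgb of at least 13 g/dL;
- a rise of more than 2 g/dL over 2 weeks (+1 week);
- a rise of more than 4 g/dL over 4 weeks (+1 week).

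The extra week reflects the permitted visit window. For the third criterion the programming note is "to look for increases > 4 g/dL over 5 weeks".

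The search for rises is then specified in two steps.

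1. **Retrieval:** "all Hgb values taken within [AE start date – 58 days, AE start date + 15 days] will be identified". The plan explains this limit as capturing "values that occurred 4 weeks before the [AE start date – 30 days, AE start date +15 days] window of interest".
2. **Pairing:** the rule applies "if there is a Hgb value (or daily Hgb average) within the [AE start date – 30 days, AE start date +15 days] window" together with an earlier value "that is within the larger [AE start date – 58 days, AE start date + 15 days] window". For the >4 g/dL criterion the permitted gap is "Between 15 days and 5 weeks, inclusive, then the Hgb values will be compared". For the >2 g/dL criterion it is "Between 1 day and 3 weeks, inclusive, then the Hgb values will be compared".

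**The concern.** The +1 week allowance was added to the interval between the two values but not to the window from which the earlier value is drawn. Some pairs that satisfy the 5-week interval, with the later value inside the window of interest, have an earlier value that is never retrieved.

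The classification feeds a formal comparison. Under SAP section 8.2.4, treatment-emergent AESIs are Tier 1 events, compared between arms by a CMH test; section 8.2.4.2 adds the relative risk and its confidence interval. The truncation can only remove qualifying events, never add them. It also leaves room for two programmers to code the rule differently, one following the 5-week interval and the other the day -58 limit.

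The affected gaps are not exotic. The schedule in SAP section 10.2.1.1 has Hgb every 4 weeks from Week 4 to Week 52, with visits at ±1 week (±3 days at Weeks 2 and 4). Gaps of 29 to 35 days between consecutive scheduled values are therefore ordinary in the first year.

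**Working it through.** **Inputs** (SAP section 10.6.4.3 unless noted; days relative to AE start)

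- Later value: day -30 to day +15, which is 46 days.
- Earlier value: day -58 or later.
- Gap for the >4 g/dL criterion: 15 to 35 days inclusive, which is 21 possible gaps.
- Gap for the >2 g/dL criterion: 1 to 21 days inclusive.
- 1 week = 7 days (SAP section 10.6.1).

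**Reproducing the plan's figure.** 30 + 4 × 7 = 58. The stated limit matches its stated basis of 4 weeks.

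**Limit needed for the stated interval.** 30 + 5 × 7 = 65. The shortfall is 65 - 58 = 7 days.

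**Which pairs are lost.** A pair is lost when (later day - gap) < -58. For each gap, the lost later-value days are:

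| Gap (days) | Lost later-value days | Number of 46 |
|---|---|---|
| 15 to 28 | none | 0 |
| 29 | -30 | 1 |
| 30 | -30 to -29 | 2 |
| 31 | -30 to -28 | 3 |
| 32 | -30 to -27 | 4 |
| 33 | -30 to -26 | 5 |
| 34 | -30 to -25 | 6 |
| 35 | -30 to -24 | 7 |

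- Total lost: 1 + 2 + 3 + 4 + 5 + 6 + 7 = 28.
- Total permitted: 46 × 21 = 966. Share lost: 28/966 = 2.9%.
- Among gaps of 29 to 35 days only: 46 × 7 = 322 pairs. Share lost: 28/322 = 8.7%.
- Worst single gap (35 days): 7/46 = 15%.
- With the limit at day -65: 0 of 966 lost.

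**Example.** Values on days -65 and -30 that differ by more than 4 g/dL meet the 5-week rule, but the day -65 value is not retrieved.

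**The >2 g/dL criterion.** The earliest day it needs is -30 - 21 = -51, which is inside the limit, so nothing is lost.

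**When a lost pair changes the classification.** The later value lies inside the window. If it is a pre-dialysis value of at least 13 g/dL, the event already qualifies. So a lost pair can matter only if the later value is below 13 g/dL, and with a rise of more than 4 the earlier value is then below 13 - 4 = 9 g/dL. In addition, no other value in the window may reach 13 g/dL, no >2 g/dL rise within 3 weeks may qualify, and no other >4 g/dL pair may be retrievable.

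**The case against.** The strongest reply is that the text is executable and deliberate. The pairing rule is a plain conjunction: later value in one window, earlier value in another, gap within limits. It gives one answer for every pair. The figure 58 is correct for its stated basis of 4 weeks, and the +1 week is described as a programming allowance for visit timing. Since the rise is meant to occur in the window around the AE, a rise from day -65 to day -30 lies almost wholly outside it, so keeping the nominal 4-week look-back could be a choice.

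Part of this stands. A reader might infer that the two provisions cannot both be applied, or that the rule is unworkable. The document does not support that: the conditions can be applied together, the full 5-week gap is usable for every later value from day -23 onward, and only an edge is cut off.

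The argument that the choice was deliberate does not hold as the text stands. The plan itself reaches back before day -30 for the earlier value, so it means to capture rises that end in the window. Nothing says that the extra week lapses for later values on days -30 to -24.

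Two other strong readings should be set aside. A reader might take the 15% as a share of events missed; it applies only to gaps of exactly 35 days and counts calendar days. A reader might also equate a missed rise with a misclassified event. The other two criteria, and any other retrievable pair including unscheduled values, can still classify the event as an AESI.

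**Conclusion.** Wrong as written: a minor internal inconsistency in a data derivation. The look-back is 7 days shorter than the interval it must serve. The loss is confined to the >4 g/dL criterion, to later values on days -30 to -24 and to gaps of 29 to 35 days, which is 28 of 966 permitted pairs (2.9%).

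These percentages weight all day-gap combinations equally. The SAP gives no Hgb data from which to estimate missed events, so the expectation that few events change status is a judgement. It rests on the other routes to classification and on the requirement that the earlier value be below 9 g/dL. That bound assumes the later value is measured pre-dialysis, as the 13 g/dL criterion requires. The same rule applies in both arms, and nothing in the document shows a differential effect. The co-primary analyses are not touched.

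**What to change.** In SAP section 10.6.4.3, replace 58 days with 65 days before AE start in both places where the limit appears: the sentence on retrieving Hgb values and the pairing rule. In the explanatory sentence after the retrieval rule, change 4 weeks before the window to 5 weeks; otherwise it would contradict the new figure.

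The gap limits stay as they are, so the wider retrieval admits no pair beyond the 5-week definition and leaves the >2 g/dL criterion unchanged.

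If the truncation was intended, keep 58 and state that the +1 week allowance does not apply in full to later values on days -30 to -24.

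Either way, the cost is a few words and, for the first option, one programming parameter. It should be settled before unblinding, because it affects which events are counted as Tier 1.
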